to translating health services research measures,⁵⁹ to translate messages to ensure that we have linguistically and culturally equivalent messages in Spanish and English. We will then pre-test the messages at the study sites with families. The research assistant will approach families after the adolescent has received an HPV vaccination, in coordination with the nursing staff. After obtaining informed consent, the research assistant will text parents in real-time, while meeting with the parent, the proposed messages and ask the parent to say back in their own words what the message means to them. This adaptation of the “teach-back” method, commonly used health literacy tool,⁵⁸ verifies that the message conveys the desired information. S/he will then ask families if there was anything confusing about the message and suggestions for change. This process will be iterative until no new changes are made to the messages. Preliminarily, we will complete this process with 20 families. If we do not reach saturation with 20 families, i.e. changes to the messages are continuing to be made, we will continue to recruit using the same sampling plan.

Study Population

Eligibility Criteria:

- Parent of adolescent age 9-17 years
- Adolescent receives their first HPV vaccine dose at study site within last 2 weeks
- Has a cell phone number that can receive a text message
- Parent speaks English or Spanish

Exclusion Criteria

- Intends to move away from the NYC area in the study

Enrollment: Families of adolescents will be enrolled one of two ways. First, they can be given an information sheet by their provider or the nurse describing the study. This will be attached to an enrollment card on which interested families can write their cell phone number. In providing their number they are agreeing to be in the study. This card will be placed in a box in the clinic. Those who do not want to enroll can indicate that as well. Those who are not given an information sheet or do not have a card in the box, due to provider time, will be called and verbal consent obtained from those who are interested.

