recruit 61.1% of eligible families. In our most recent text message vaccine related study in which we completed active recruitment, 92% of eligible patients enrolled. We therefore believe our enrollment goal is realistic. At the study sites, 35% of 11–17-year-olds who initiate HPV vaccination and receive usual care receive 3 doses within 12 months. In our previous study, we had an effect size of 16% between those receiving conventional text messages and usual care. Therefore, based on this data, we expect a completion rate of 51% in the conventional group (Arm 2). With the proposed sample size in each arm and allocation, we will be powered to detect a minimum of 9% difference between arms with 80% power, allowing for a type I error of 5% for the primary outcome. In our second dose influenza vaccine study (section D3.1), our effect size was 9% between each arm; we expect the effect size in this trial to be higher since the messages will be personalized.

Intervention and Usual Care: The study will include approximately 30 months of recruitment. The intervention period for each individual is the 12-month period starting from administration of their first dose, as is standard in studies assessing HPV series vaccine completion as well as the efficacy trials.^{37,39,50,60-62}

Arm 1: Randomized to receive additional enhanced text messages with vaccine health literacy-promoting information: An interactive query sent before the next dose is due will assess whether a parent is in the pre-contemplation stage and unaware their adolescent needs another HPV dose or when the dose is due, or if they are in the contemplation stage knowing that their adolescent needs further doses, but still undecided maybe due to questions regarding the vaccine efficacy, side effects and safety, or if they are in the preparation phase and planning to vaccinate but still in need of information on where to go or when. These will be based on previously published HPV vaccine decisional measures that used the trans-theoretical model.²⁶ Messages will then be tailored to their stage. In addition, we will include interactive text messages in the series that will allow participants to select to receive more information according to their specific needs, allowing self-tailoring of the text messaging. Finally, the current health literacy recommendations include “universal precautions” with all patients receive health literacy-promoting information regardless of perceived risk for limited health

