
If the site does not have vaccine, we will send a message to participants due for second or third dose letting them know not to come in yet and that we will inform them when the sites have vaccine available again.

Measures

Outcome Measure: The primary outcome measure is completion of the 3-dose HPV vaccine series within 12 months from date of first dose. A secondary outcome is timeliness of vaccination, defined as time elapsed in days between dose 1 and 2, and dose 1 and 3.

Process Measures: Individual level information from the log files of the text-messaging platform will be collected to demonstrate that the correct messages were sent to each recipient for Arms 1 and 2. We will also determine the percentage of (1) text messages that sent back as undeliverable; and (2) participants opting out of the reminders during the study. We will also determine which specific vaccine health literacy-related information families request via text message, providing, in a prospective fashion, an indication of the most common parent identified HPV vaccine health literacy needs arising at the time that parents are making decisions regarding return for subsequent doses. This prospective information does not currently exist.

Follow-Up: Minimizing attrition and missing outcome data are crucial for valid results. We expect there will be little attrition with respect to outcome data. The hospital immunization registry, EzVac, automatically collects vaccine administrations from the EHR used at the 4 study sites as well as from the New York Citywide Immunization Registry (CIR) as part of the usual patient care, thereby allowing capture of vaccines administered to clinic patients both at study sites and at practices other than study sites in NY City.^{55,56} Thus, we will have outcome data for subjects who receive HPV vaccination at facilities other than a study site. A second important issue is documentation of the intervention. In our previous HPV study, no one dropped out of the study after enrollment;²⁰ in our influenza text message RCT, only 4.5% of the 9,213 families declined further messages.¹³ In addition, we expect only a small number of cell phone numbers will change over the course of the intervention. In our previous adolescent study, the number of cell phone numbers that changed was <2%.¹⁴

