Data Management: Vaccination data will be retrieved from EzVac. All data will be accessed using a password-protected computer in a locked office and stored on a secure server managed by Columbia University IT, and backed up on a daily basis. All data files will be cleaned and edited prior to analysis, under [name] supervision. Data analysis will be performed using SAS (Cary, NC). The programmer will monitor log files of text messages sent, replies received, and "undeliverable" messages and provide summaries to [name] on a daily basis.

Statistical Procedures

Data Analysis: We will first assess the randomization process by comparing baseline variables among the three groups. Hypothesis: Completion and timeliness will be higher in adolescents in families who receive enhanced text message reminders plus usual care vs. non-enhanced text message reminders plus usual care.

Series Completion: HPV vaccine completion rates in EzVac will be compared for all adolescents of participant parents at the end of a 12-month observation period starting at receipt of their first HPV vaccine dose. As in our previous RCT of influenza vaccine reminders,¹³ all primary analyses will be done on an intention-to-treat basis, such that all randomized participants will be included in the analysis whether or not they at some point declined further messages or messages were returned as undeliverable. A secondary analysis will compare completion rates for adolescents of participants who received the entire set of reminders. Study arms will not be combined. Completion rates in the two randomized groups will be compared in the separate combinations delineated above using 2-sided 2 tests at a significance level of $P<0.05$ for each comparison. The number of subjects in each cell is expected to be high enough that the Fisher exact test will not be needed. Asymptotic confidence limits on the differences and relative rate ratios will be calculated.

Sub-group Analyses: We will perform subgroup analyses in different covariate-defined subgroups, for each outcome, to assess the possibility of intervention effects being different in these subgroups. This will be tested by including pre-specified covariates (adolescent: age, gender, year of entry, clinic site, dichotomized visit count; parent: language, previous participation in text message vaccination reminder study),^{42,43,60,61,64-}

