⁶⁸ and their interactions with the intervention in a multiple logistic regression analysis. The models will also adjust for the direct effects of these covariates on the outcomes, thus increasing power to detect intervention effects. Initial models will be created including all of these covariates. Clearly non-significant ($p>0.2$) covariate terms will be removed from the final models. If more than one covariate appears in a final model, two-way (and, if necessary, multi-way) interactions of those covariates among themselves and with the study arm will be tested and included if significant at $p>0.2$) covariate terms will be removed from the final models. If more than one covariate appears in a final model, two-way (and, if necessary, multi-way) interactions of those covariates among themselves and with the study arm will be tested and included if significant at $p<0.05$. In addition to the covariates listed above, we will include race and insurance to the extent possible. Multivariate modeling with these covariates may not be possible depending on the degree of variability observed. The visit count will be defined as the number of clinic visits per adolescent in the 12-month period post-receipt of the first vaccine dose. Visits to the emergency department, hospitalization or specialty visits will not be included. The visit count will be dichotomized (the cut point determined by the frequency distribution of visit counts). With regard to longitudinal measurement, the outcome is defined as success or failure in receipt of 3 HPV vaccine doses within 12 months (no repeat measure of outcome). We will include a covariate for year of entry into study. We will also adjust for vaccine shortages as needed.

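### The visit-count covariate is measured over the intervention and outcome window, so the secondary adjusted, subgroup and Cox arm effects condition on a post-randomisation variable

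*Combined protocol and SAP*

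**What the plan says.** Sub-group Analyses (under Statistical Procedures) lists the pre-specified covariates, among them "adolescent: age, gender, year of entry, clinic site, dichotomized visit count". These enter a multiple logistic regression as main effects and in interaction with the intervention. Adjustment for them is justified as "thus increasing power to detect intervention effects".

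The count is then defined: "The visit count will be defined as the number of clinic visits per adolescent in the 12-month period post-receipt of the first vaccine dose". The only exclusions are these: "Visits to the emergency department, hospitalization or specialty visits will not be included". The cut point is to come from the observed distribution of counts.

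Model reduction follows the rule "Clearly non-significant ($p>0.2$) covariate terms will be removed from the final models"; the test behind that p-value is not named. Interactions are kept at p<0.05. The Timeliness section carries the same covariates into Cox models.

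Three other statements fix the time frame:

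- Intervention and Usual Care: "The intervention period for each individual is the 12-month period starting from administration of their first dose".
- Outcome Measure: "The primary outcome measure is completion of the 3-dose HPV vaccine series within 12 months from date of first dose".
- Eligibility Criteria: "Adolescent receives their first HPV vaccine dose at study site within last 2 weeks".

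The plan gives no pre-dose version of the count and no analysis without it.

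**The concern.** A covariate used to sharpen a randomised comparison should be fixed before randomisation. This one accrues almost entirely afterwards, and two routes link it to what is being estimated.

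1. **It can record the outcome.** The sites give doses 2 and 3 at walk-in visits, and the exclusions do not remove them. An adolescent who completes on site adds two visits to the count by doing so.
2. **The arm can change it.** Reminders aim to bring families back. Visits that the enhanced messages prompt are part of the effect, and adjusting for them removes that part. If unmeasured engagement drives both visits and completion, adjustment can also create an arm difference where none exists.

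In the Cox models there is a further fault: a fixed 12-month count includes visits made after the event, so the hazard is conditioned on the future.

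At stake are the secondary adjusted arm effect, the visit-count subgroup result and the adjusted hazard ratios. A reader could not separate an arm effect from an artefact of conditioning on attendance.

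**Working it through.** **Share of the window after randomisation.** Dose 1 is at most 2 weeks before enrolment, and the Enrollment text allows about one more week for re-sent confirmation messages. If randomisation follows promptly, at least (52 − 3)/52 = 94% of the window comes after it.

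**The plan's own figure.** Inputs from Study Sample and Enrollment: 51% versus 60%, two-sided 5%, 80% power, 1:1.

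n per arm = [1.96·√(2·0.555·0.445) + 0.8416·√(0.51·0.49 + 0.60·0.40)]² / 0.09² = (1.3775 + 0.5891)² / 0.0081 = 477.5, so 478. This matches the plan (956 in total).

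Unadjusted OR = (0.60/0.40)/(0.51/0.49) = 1.441, log OR 0.3655. SE = √[(1/0.2499 + 1/0.24)/478] = 0.1307, z = 2.80, power 80%.

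**Method for the adjusted test.** The documents give no visit rates, so what follows is illustrative. A logistic model with arm and high/low visits was fitted to expected counts at n=956, with a two-sided 5% Wald test.

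**Case A: dose visits are counted.** Assume other visits are Poisson with mean 0.5 to 3, completers add 2 dose visits, and half of non-completers add 1. Splits are at and just above the pooled median.

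Worked example, mean 1, high = 3 or more:

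- P(high | completer) = P(Poisson(1) ≥ 1) = 0.632.
- P(high | non-completer) = 0.5·0.264 + 0.5·0.080 = 0.172.
- Low stratum: Arm 2 completion = 0.51·0.368/(0.51·0.368 + 0.49·0.828) = 0.316; Arm 1 = 0.400. OR = (0.400/0.600)/(0.316/0.684) = 1.44.
- High stratum: 0.792 and 0.846. The OR is again 1.44.

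The OR holds because visits depend on arm only through completion, so the factor P(high | completer)/P(high | non-completer) cancels between arms. Precision does not hold:

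- n·p·(1−p) is 61.3 (Arm 2) and 63.3 (Arm 1) in the low stratum, and 32.0 and 27.9 in the high stratum.
- Combined information = 61.3·63.3/124.6 + 32.0·27.9/59.9 = 31.1 + 14.9 = 46.0.
- SE = 1/√46.0 = 0.147, z = 2.48, power 70%.

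In the 8 of 10 splits where the low stratum contains completers (24-44% of it), the OR is 1.44 and power is 70-76%. In the other two (means 0.5 and 1, high = 2 or more) the low stratum has no completers, since on-site completion itself takes two visits. The interaction is then inestimable unless off-site completions fall there.

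**Case B: dose visits are not counted, visits are prognostic.** logit(completion) = a + g·visits + d·arm, with g = 0.3, 0.5 or 0.8, Arm 2 mean 3.0 visits, and high = 3 or more or 4 or more. The Arm 1 mean is set so that a given share of the 9 points runs through visits.

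| Share through visits | Arm 1 mean | Adjusted OR | Power |
|---|---|---|---|
| 0% | 3.0 | 1.46-1.57 | 81-87% |
| 25% | 3.16-3.32 | 1.37-1.46 | 66-73% |
| 50% | 3.32-3.65 | 1.29-1.35 | 47-54% |

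The 0% row exceeds 1.44 through non-collapsibility of the OR and is the right comparator for the other rows.

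**Case C: the count is neither prognostic nor changed by arm.** OR 1.44, power 80%, no loss.

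**No true effect.** In simulations of 400,000 subjects, engagement drove both visits and completion and the arm raised the visit rate by 10-35%. The adjusted OR was 0.96 to 0.89, against 0.99-1.00 unadjusted: an apparent harm from adjustment alone.

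**The p>0.2 rule.** In simulated trials of n=956 it removed the term in 0% of trials in cases A and B, and in 79-81% in case C, where the term is harmless. With no completers in the low stratum it removed the term in 100% of trials by the Wald p and 0% by the likelihood-ratio p, so no power figure is given for that situation.

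**The case against.** The best-documented route, case A, does not bias the odds ratio, which is the measure the planned logistic model reports. It costs precision and creates no false interaction on that scale. The plan's p<0.05 rule for interactions also limits what reaches a final model.

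Bias in the OR needs case B, in which Arm 1 attracts more non-dose visits than Arm 2. Both arms receive messages in parallel timing, the messages concern HPV doses, and nothing in the documents suggests that Arm 1 raises other attendance. With no mediation, case B delivers the power gain the plan promises (81-87%). The stratum without completers arises in only 2 of 10 assumed splits with all doses on site, whereas off-site doses are captured through the city registry. The Cox fault has not been quantified.

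All of this stands as a limit on size, and the 0% row belongs in the range shown. It does not make the covariate a baseline one. Whether the arm changes attendance is unknown before the trial, and the definition leaves the analysis exposed to it. The elimination rule gives no protection, because it keeps the count when the count is strongly related to completion.

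**Conclusion.** The concern holds. The visit count is a post-randomisation variable used as an adjustment and interaction term in the secondary logistic and Cox models, and nothing in the plan corrects for this. That much follows from the text alone.

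The size is not determined. Across the prognostic or outcome-recording cases, power of the secondary adjusted test runs from 47% to 87% against 80% unadjusted, and the OR from 1.29 to 1.57 against 1.44. The stated power gain is therefore not assured for this covariate. These ranges rest on assumed visit rates, prognostic strength and mediated share, on all doses being given on site, and on a 3-dose outcome for everyone; the two-dose change dated 10/21/16 is not modelled.

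The unadjusted intention-to-treat comparison, the Kaplan-Meier and log-rank analysis and the sample size of 478 per arm do not use the count and are unaffected. The sponsor should correct this, but it does not threaten the primary result.

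**What to change.** - Define the visit count over the 12 months before dose 1, at the same clinics and with the same exclusions, leaving out the dose-1 visit.
- Set the cut point on the pooled baseline distribution before the models are run.
- Use this count in the logistic, interaction and Cox models.
- If pre-dose records are not available, drop the visit count from every model that estimates the arm effect.
- Report the post-dose count by arm as a descriptive process measure only, stating whether vaccine-only visits are included.

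The cost is two or three lines of SAP text and one extra data pull. The documents do not say whether pre-dose visit records exist, so their availability is assumed. Adolescents new to the clinic will have low or zero counts, and a pre-dose count may be less prognostic, so no particular power gain should be promised.

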We will identify in EzVac those who received their first HPV vaccine in approximately the last week for whom we do not have a card. On inclusion, either via return of the enrollment card or over the phone, a confirmation text message will be sent to the participant family and delivery status assessed to ensure that the family has a working cellphone with text message. An undelivered message will be attempted to be delivered twice moreover the next week. If there are three undeliverable messages then the family will not be considered to have met eligibility criteria and will not be considered enrolled in the trial; they will be notified of this. We will enroll only one child per family. If more than one is eligible, we will select the one with the next most proximal birthday, e.g. a child whose birthday is in 7 days will be selected over a sibling whose is in 75 days. In the case of twins, whoever was designated at birth as twin A will be enrolled. If another adolescent becomes eligible during the trial, the family cannot re-enroll.

Randomization: Randomization will occur with a 1:1 allocation ratio stratified by (1) clinical site; (2) adolescent's gender; (3) parental language; and adolescent's age group (9-14; 15-17). These factors will be excerpted from the medical record after enrollment. Randomization will be done centrally by the programmer using an algorithm based on site, gender, language, and age. The statistician and analyst will be kept blinded to group assignment.

Study Sample and Enrollment

Based on EzVac data, there were 817 adolescents (females and males) 11-17 years old who received their first HPV vaccine at the four study sites between October 2012 and September 2013. Nearly all of those families (n=805) spoke English or Spanish. A few (n=51) were from the same family. Therefore, we expect 1885 adolescents to be eligible over the 30-month recruitment period. Across various studies conducted at the study sites, we found that between 83% and 89% of parents had text messaging. In one study, we assessed those with and without text messages and found no significant differences between those who had texting and those who did not in terms of adolescent's gender, parents' primary language, education level, or parent age. Using the low-end of this range, i.e. 83%, we expect 1,564 families to meet age, language and cell phone/texting inclusion criteria. To meet our sample size of 956 total (478 per arm), we would need to

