Missing data: We will document missing data and classify it by variable and study arm. We will then assess if there are relationships between missingness and covariates such as demographics, study arm, or year of study entry. In the analysis of the study hypotheses, all randomized subjects will be included (intention to treat analysis). Missing outcome data will be imputed as failure in all study arms. We anticipate very few subjects will be missing outcome data. In the subgroup analyses, covariate data may also be missing. We will impute these variables using multiple imputation following the methodology of Rubin.⁷¹ We will achieve this using the 3-phase SAS/STAT procedure that first creates “m” multiply imputed complete data sets using the MI procedure, then analyzes the “m” complete datasets using a standard procedure, PROC LOGISTIC, and finally generates valid statistical inferences about the missing values by combining the results using the MIANALYZE procedure properly reflecting the uncertainty due to missing values. In summary, the primary analysis of the study hypotheses will be based on intention to treat analysis using all randomized subjects. Subjects with missing outcome data will be retained in the analysis; failure to complete the 3-dose series will be imputed for those missing these data. We consider this to be the most conservative approach to hypothesis testing. We used this approach in our influenza-vaccine text message reminder study.¹³ Multiple imputation will be used for the missing covariate data in subgroup analyses.

In addition as of 10/21/16: Any parents of an adolescent who was <15 years when first vaccinated who is already enrolled and has not yet received their second dose, will get a text message letting them know that there is an important update, that their child now only needs two doses with the second one being 6 months after the first and that we will text them when that dose is due. We have included that text message under documents.

Parents of adolescents first vaccinated before 15 years of age who have not yet received a second dose will receive an updated series of messages to be consistent

with the now 2 dose recommendation in both phrasing and timing (second dose now due 6 months after the first instead of 2 months and is now the last dose.

Recruitment And Consent

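### Subgroup models carry calendar time only as year of entry, so the arm-by-age and arm-by-year tests can mistake the 10/21/16 schedule change for effect modification

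*Combined protocol and SAP*

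**What the plan says.** Statistical Procedures, Sub-group Analyses, sets out a multiple logistic regression with arm-by-covariate interactions: "This will be tested by including pre-specified covariates (adolescent: age, gender, year of entry, clinic site, dichotomized visit count", followed by parent-level covariates. Age and year of entry are both listed, so arm-by-age and arm-by-year tests are planned. The section adds: "We will include a covariate for year of entry into study". Its only other time-related item is adjustment for vaccine shortages as needed. Covariate terms with p>0.2 are dropped from final models. Multi-way interactions are tested only if needed.

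The Timeliness section uses the same covariates in Cox models for time from dose 1 to dose 2 and from dose 1 to dose 3.

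The text dated 10/21/16, placed after Missing data, changes the schedule for one group: "Parents of adolescents first vaccinated before 15 years of age who have not yet received a second dose will receive an updated series of messages". For them dose 2 moves from 2 to 6 months after dose 1 and becomes the last dose. Outcome Measure and Sub-group Analyses still define success as 3 doses within 12 months for everyone.

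**The concern.** The schedule change is an event defined by age, date and dose-2 status. Year of entry is a single term across all ages, so it cannot represent that event. Adolescents aged 15-17 are unaffected in every year, while under-15s within one entry year can be followed under either schedule. The age boundary of the change is also the boundary of the randomisation strata (9-14; 15-17), so an arm-by-age contrast overlaps with an arm-by-schedule contrast.

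If the arm effect differs by schedule, the trial could report that the enhanced messages work less well in younger adolescents, or that their effect faded over entry years, when only the number and timing of doses due had changed. In the Cox models, the dose-2 due date moves by four months for one age group from one date, and switched families have no third dose due.

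**Working it through.** **Planned effect.** "To meet our sample size of 956 total (478 per arm), we would need to" recruit 61.1% of eligible families. "we expect a completion rate of 51% in the conventional group (Arm 2"), and "we will be powered to detect a minimum of 9% difference between arms with 80% power, allowing for a type I error of 5"%. Tests are two-sided ("using 2-sided 2 tests at a significance level of" P<0.05) and allocation is 1:1 ("Randomization will occur with a 1:1 allocation ratio stratified by (1) clinical site"). With pooled variance under the null:

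n per arm = [1.96·√(2·0.555·0.445) + 0.842·√(0.51·0.49 + 0.60·0.40)]² / 0.09² = 477.5, rounded up to 478. The plan's figure is reproduced, so 51% vs 60% is the planned three-dose effect, with odds ratio (0.60/0.40)/(0.51/0.49) = 1.44.

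**Does year of entry line up with the change?** Assume uniform entry and a 365-day window. For under-15s:
- 2015 entrants: 294/365 = 81% have windows closed before 10/21/16, and 19% straddle it.
- 2016 entrants: 294/366 = 80% straddle it, and 20% start on or after it.
- 2017 entrants: 100% start after it.

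The documents give no recruitment start date. For assumed starts of the 30-month recruitment from 10/2014 to 12/2015, the shares run from 42% to 0% closed, 40% to 36% straddling and 18% to 64% after. Straddling is not the same as switched, because an adolescent who already has dose 2 is not switched.

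**Effect on the completion model, 3-dose outcome as written.** Assume half of under-15s are switched, switched families do not reach 3 doses in either arm, and there is no true modification by age or year.
- Under-15s: 0.5·51% = 25.5% vs 0.5·60% = 30.0%; difference 4.5 points, odds ratio 1.25.
- 15-17s: 51% vs 60%; difference 9.0 points, odds ratio 1.44.

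The difference in log odds ratios is 0.366 − 0.225 = 0.141. Its standard error is √Σ 1/(n·p·(1−p)) over the four arm-by-age cells. With N = 956 and 50% under 15 (239 per cell) this is √(0.0220 + 0.0199 + 0.0167 + 0.0174) = 0.276, giving z = 0.51 and 8.0% two-sided rejection. With 75% under 15, rejection is 7.4%; with 90%, it is 6.2%. The age mix is not in the documents.

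With other switched shares, under-15s show 6.7 points (odds ratio 1.32) at 25% and 2.2 points (1.21) at 75%.

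**Same, with switched families scored on two doses.** Assume equal return probability per dose: √0.51 = 71.4% and √0.60 = 77.5%.
- Under-15s, half switched: (51 + 71.4)/2 = 61.2% vs (60 + 77.5)/2 = 68.7%; 7.5 points, odds ratio 1.39.
- A wholly two-dose group: 6.0 points, odds ratio 1.38.

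Against 1.44 in 15-17s, the log odds ratio difference is 0.034 and rejection is 5.1-5.2% over the same age mixes.

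**Simulation under different assumptions.** Change at month 15 of 30, 75% under 15, 60% eventually receiving dose 2, and 2% three-dose completion after the change in both arms. With an arm effect that depends only on schedule, arm-by-year rejects about 8% and arm-by-age about 14%. A 15-point effect, larger than the planned 9, raises these to about 15% and 30%. Adding schedule-period terms fixed at dose 1, with their arm interactions, returns both to about 4-6%. If the arm odds ratio is the same under both schedules, rejection stays at 5-6% without those terms. Some replicates did not converge, so these rates are approximate.

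**The case against.** The best defence is that this is mostly a consequence of a more basic conflict: a 3-dose outcome is kept for families told that two doses suffice. That largely stands for the completion model. The plan tests interactions by logistic regression, and on the odds-ratio scale the artefact nearly disappears once switched families are scored on two doses. A reader might infer that the problem is as large whatever outcome is used; the arithmetic does not support that.

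The plan also allows multi-way interactions, so an arm-by-age-by-year term could absorb part of the change. That provision is conditional, and it cannot separate entry years that contain the date. The shortage adjustment is not a schedule term. Approach Overview foresees analysing an effect on 2 doses but specifies no model.

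These are also subgroup and secondary analyses. A reader might infer that the primary comparison is biased. It is not confounded, because the change applies to both arms, although with the 3-dose outcome it is diluted. Nor does the plan claim that year of entry handles the schedule change. Sub-group Analyses lists age without saying it is modelled as 9-14 vs 15-17, so the overlap with the change depends on how age is coded.

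**Conclusion.** The gap is real and worth closing, but modest. As written, the arm-by-age and arm-by-year tests compare mixtures of schedules and can attribute a schedule effect to age or entry year. It would overstate the point to say that they compare three-dose with two-dose follow-up outright: 15-17s stay on three doses throughout, and some under-15s do too.

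For completion, the planned effect with half of under-15s switched gives about 6-8% rejection of arm-by-age with the 3-dose outcome and about 5% with two-dose scoring of switched families. In the second case the issue is mainly interpretation. These figures rest on assumed switched shares, age mix and per-dose return. Misattribution also requires the arm effect to differ by schedule on the odds-ratio scale. The Cox exposure follows from the changed due dates and has not been quantified.

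**What to change.** In Sub-group Analyses and Timeliness, keep age and year of entry and add a schedule-era variable fixed at dose 1, with its arm interaction. It crosses age (<15, 15-17) with dose-1 date: 12-month window closed before 10/21/16, straddling it, or dose 1 on or after it. If age enters as the same two groups, code the era as indicators for under-15 straddling and under-15 after, to avoid redundancy. Exempt these terms from the p>0.2 removal rule. Do not use the schedule actually followed, because it depends on dose-2 status after randomisation.

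Report arm-by-schedule-era as its own labelled contrast, and interpret arm-by-age and arm-by-year only from the model containing it. Where numbers allow, add two sensitivity analyses: arm-by-year in 15-17s only, and arm-by-age in windows closed before the change. If no under-15 windows closed before it, as at the latest assumed start, arm-by-age cannot be separated from schedule and should be declared not estimable.

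Separately, reconcile the 3-dose outcome in Outcome Measure and Sub-group Analyses with the two-dose schedule in the 10/21/16 text.

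The cost is SAP wording and one variable derived from age and dose-1 date, both already held. The downside is less precise age and year interaction estimates.
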